8.1 Primary safety endpoint

All RA-related complication rate

8.2 Safety index

The following safety data will be collected over the 12-months follow-up period:

1. All-cause death (cardiac/non-cardiac/sudden death/unknown)
2. Myocardial infarction
 - a. Subset analysis on target vessel MI (TVMI) in those with data on repeat coronary angiography
3. Target lesion revascularization (TLR)
4. Definite/probable stent thrombosis
5. Major cardiovascular events (MACE)
 - a. Defined as composite endpoint of cardiac death, MI, TLR, and stent thrombosis
6. Stroke
7. Device related adverse events
 - a. Includes but are not limited to rotawire fracture/ breakage, rotawire unravelling/ fraying, burr dislodgement/ fracture and burr entrapment

8.2 Reporting of adverse events

The events listed in Section 12.1 are all considered serious adverse events (SAE). However, as the procedure is done in accordance to standard of care and RA has been extensively used in clinical settings worldwide, these safety data will only be collected for the purposes of this registry and does not require safety reporting to Institutional Review Board (IRB) or Ethics Committee (EC).

Should there be an SAE deemed reportable by the respective site PI, the site PIs are to report the event(s) to their respective local IRB or EC as per their own prevailing safety reporting guidelines.

9. Data management/ monitoring

9.1 Accountability of data, completion and handover of data entry form

All participants who have signed the study consent form and are eligible for participation will have all of the necessary information recorded in the data entry form.

9.2 Database design

A secure web-based database application i.e. REDCap will be used to collate study data and for the purposes of study analysis.

9.3 Data entry

Clinical research coordinator (CRC) and/or authorized study investigators will be able to input and edit the data from the case reporting form into the electronic database as accurately as possible.

9.4 Data verification

The database will be reviewed by the site investigators as well as lead investigators to ensure the veracity of the data collected. If there are any discrepancies noted, a manual enquiry will be raised and will be discussed between involved study sites and the primary study site i.e. NHCS.

9.5 Data security

After the CRC or researcher fills in the data completely, data managers, statisticians and lead PI will review the data and finalise the analysis/ outcomes of the study population before locking/ encrypting the database.

10.1 Sample size determination

10.1.1 Statistical hypothesis

The RA-related complications occur in 5% of all the RA procedures in Asian PCI centres

NOTE: See Appendix 1 and 2 for contemporary data on RA-related complication rates justifying selection of 5% incidence rate for all RA-related complications³¹.

10.1.2 Assumptions

The target sample size is calculated based on the following assumptions:

1. The proportion of RA-related complications is 5%
2. 95% confidence intervals width is 3%.
3. Up to 20% of patients are assumed to drop out of this study

Sample							
Confidence	Size	Target	Actual	Proportion	Lower	Upper	Width if
Level	(N)	Width	Width	(P)	Limit	Limit	P = 0.5
0.95	1118	0.02	0.02	0.03	0.02	0.04	0.059
0.95	1476	0.02	0.02	0.04	0.03	0.05	0.051
0.95	1825	0.02	0.02	0.05	0.04	0.06	0.046
0.95	2167	0.02	0.02	0.06	0.05	0.07	0.042
0.95	497	0.03	0.03	0.03	0.015	0.045	0.088
0.95	656	0.03	0.03	0.04	0.025	0.055	0.077
0.95	811	0.03	0.03	0.05	0.035	0.065	0.069
0.95	963	0.03	0.03	0.06	0.045	0.075	0.063
0.95	280	0.04	0.04	0.03	0.01	0.05	0.117
0.95	369	0.04	0.04	0.04	0.02	0.06	0.102
0.95	457	0.04	0.04	0.05	0.03	0.07	0.092
0.95	542	0.04	0.04	0.06	0.04	0.08	0.084

Table 1: Numeric Results for Two-Sided Confidence Intervals for One Proportion Confidence Interval

Formula: Simple Asymptotic

10.1.3 Final sample size

1000 subjects

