3.3 Exit criteria

Participation in this study is optional and patients are free to withdraw their participation from this study at any time point during the study process without the need to provide any justification. Withdrawal from this study will not affect participants' future medical treatment.

Patients who have withdrawn their participation are not obligated to continue further follow-up and will not be replaced by new participants in this study. A reasonable sample size has been calculated to account for patient attrition.

Should the reason for withdrawal from the study be due to issues related to either safety or effectiveness of the study device, the investigator shall obtain a new separate consent from the subject, independent of the original study consent, to continue tracking his/her clinical progress/ situation.

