15.2 Appendix 2: Definition and breakdown of RA-related complications

Paper	Study	Modality	Definition	Outcomes in RA
Safian et. al CARAT trial CCI 2001	Prospective, randomised, multicenter	RA (large vs small burr)	Any of (i) severe dissection (ii) no reflow (iii) side branch occlusion	Total 12.1%; severe dissection 6.3%, no reflow (2.3%), sidebranch occlusion (3.5%)
				Breakdown by burr size: large (12.7%) vs small (5.1%), p < 0.05
Abdel-Wahab et. al PREPARE CALC trial CCI 2018	Prospective, randomised, multicenter	RA vs modified balloon (MB)	Any of (i) large dissection (ii) perforations (iii) no/slow reflow (iv) side branch occlusion	Large dissection (3%), Perforation (4%), No/slow reflow (2%), side branch occlusion (6%)
Lee et. al AJC 2017	Retrospective, single center	RA vs OA	Any of (i) perforation (ii) dissection leading to less than TIMI 3 flow (iii) no reflow	Perforation/ dissection (0%), no- reflow (7%)
Chen et. al. J Interven Cardiol 2018	Retrospective, single center	RA of main vessel (MV) vs side branch +/- main vessel (SB-MV)	Any of (i) No flow (ii) SB perforation (iii) Wire transection	No flow in SB (4.2%) vs SB-MV (2.9%), perforation in SB (6.3%) vs SB-MV (0.8%), wire transection SB (0%) vs SB-MV (0.8%)

Breakdown by each complication:

- (i) Severe dissection: 1.7 – 5.9%
 - a. Lee et. al AJC 2017: any dissection that resulted in < TIMI 3 flow
 - b. Safian et. al CARAT trial 2001: any dissection that requires stenting
 - c. Abdel-Wahab et al. PREPARE-CALC 2018: large dissection > 5mm
 - d. Ali et. al DISRUPT CAD II 2019: any dissection Type D-F that impaired flow
 - e. NHLBI (based on depth and breadth of dissection + presence of intimal flap)

The National Heart, Lung and Blood Institute (NHLBI) classification system for intimal tears

Type A dissections represent minor radiolucent areas within the coronary lumen during contrast injection with little or no persistence of contrast after the dye has cleared

[figure not shown]
Type B dissections are parallel tracts or a double lumen separated by a radiolucent area during contrast injection, with minimal or no persistence after dye clearance

Type C dissections appear as contrast outside the coronary lumen ("extraluminal cap") with persistence of contrast after dye has cleared from the lumen

Type D dissections represent spiral ("barber shop pole") luminal filling defects, frequently with excessive contrast staining of the dissected false lumen

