Type E dissections appear as new, persistent filling defects within the coronary lumen

Type F dissections represent those that lead to total occlusion of the coronary lumen without distal antegrade flow

- (ii) Slow flow/ no reflow: 2.5%
- (iii) Perforation: 2%
 - a. All papers did not define/ classify perforation type. They included all types of perforation in analysis for complications

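### The 3% interval width for the primary safety endpoint rests on a 5% complication rate that most of the protocol's own appendix data exceed

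*Protocol*

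**What the plan says.** The sample size is built on precision, not on a test. Section 10.1.2 lists three assumptions: "The proportion of RA-related complications is 5" (percent), "95% confidence intervals width is 3" (percent) and "Up to 20% of patients are assumed to drop out of this study". Its Table 1, captioned "Numeric Results for Two-Sided Confidence Intervals for One Proportion Confidence Interval", uses the simple asymptotic formula and gives 811 patients for a 5% rate and a 0.03 width. Section 10.1.3 then gives "1000 subjects" without showing the step from 811. Section 3.3 adds that "A reasonable sample size has been calculated to account for patient attrition" and that withdrawn patients are not replaced.

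The support for 5% is in Section 10.1.1, which points to Appendices 1 and 2 and to a cited review article. The breakdown at the end of Appendix 2 reads "Severe dissection: 1.7 – 5.9" (percent), "Slow flow/ no reflow: 2.5" (percent), and perforation 2%.

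The primary safety endpoint (Section 8.1) is the rate of all RA-related complications. That section gives neither a component list nor a time window. Perforation and no-reflow or slow flow are counted within 48 hours as secondary outcomes (Section 7.2). Device-related events are collected over 12 months (Section 8.2, Safety index). The safety analysis set (Section 10.2) takes every subject evaluated at least once for safety.

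**The concern.** The 3-point width is the only quantitative design target in the protocol, and it belongs to the primary safety endpoint. The width of an interval for a small proportion grows with the proportion, so the target depends on the assumed rate. If the sources cited for 5% mostly show something higher, readers are promised tighter precision than the registry is likely to give. The protocol does not show how the component rates were combined to reach 5%.

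The 20% loss also needs a stated basis. Follow-up after the procedure is a telephone contact at 12 months (Section 4.2.2). Loss before that call is not obviously loss of a complication recorded around the procedure.

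**Working it through.** **Reproducing the plan's figure.** For a simple asymptotic 95% interval of full width W, n = 4 z² p(1−p) / W², with z = 1.96. At p = 0.05 and W = 0.03 this gives 810.97, so 811, as in Table 1. All twelve rows of Table 1 reproduce. Allowing for 20% loss, 811 / 0.8 = 1013.75, so 1014. The protocol has 1000, which leaves 800 at a full 20% loss.

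**Rates in the cited appendices.**

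- *Appendix 2 breakdown.* Low end: 1.7 + 2.5 + 2 = 6.2%. High end: 5.9 + 2.5 + 2 = 10.4%. These sums assume that no patient has two events, so they are upper bounds for these three components. Side-branch occlusion and device events are not included.
- *Limits of overlap.* A composite cannot be below its largest component. At the low dissection rate it lies between 2.5% and 6.2%, which includes 5%. At the high dissection rate it lies between 5.9% and 10.4%, which does not.
- *Trial of large versus small burrs (Appendix 2).* Composite 12.1% = 6.3 + 2.3 + 3.5. Severe dissection alone is 6.3%, above the top of the range in the breakdown.
- *Other single components in Appendix 2.* Side-branch occlusion is 6% in the trial against modified balloons. No-reflow is 7% in the retrospective comparison with orbital atherectomy.
- *Dissection in Appendix 1.* It is 7.0% in the study of 1176 patients. Over the ten studies reporting it, rate × n adds to about 132.8 events in 2553 patients, or 5.2%. The largest study drives this: without it, (132.8 − 82.3) / (2553 − 1176) = 50.5 / 1377 = 3.7%.
- *Three components in Appendix 1.* Seven studies report dissection, perforation and slow flow/no reflow. The sums are 4.0, 4.3, 5.0, 6.9, 9.0, 9.1 and 10.5%. The three at or below 5.0% hold 50 + 95 + 120 = 265 of the 2137 patients.

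**Width at those rates.** W = 2 z √(p(1−p)/n):

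| Rate | Width, 800 evaluable | Width, 1000 evaluable | Evaluable needed for 3 points |
|---|---|---|---|
| 5% | 3.02 | 2.70 | 811 |
| 6.2% | 3.34 | 2.99 | 993 |
| 7.0% | 3.54 | 3.16 | 1112 |
| 10.4% | 4.23 | 3.78 | 1591 |
| 12.1% | 4.52 | 4.04 | 1816 |

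**Where the target fails.** Setting W = 0.03 and solving for p gives 4.93% with 800 evaluable and 6.25% with 1000.

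**The case against.** **A stronger reading.** A reader might infer that 1000 fails on the plan's own inputs, since 800 is below 811. The documents do not support treating that as a sample-size error. The 20% is an upper bound, and a loss of 18.9% leaves exactly 811. The width at 800 is 3.02 points, which is 0.03 at the precision Table 1 prints. If every patient counts for complications around the procedure, the width at 5% is 2.70, better than the target. The 14-patient gap is a rounding remark, and Section 3.3 is substantially right that attrition was allowed for.

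**Support for 5%.** A reader might also infer that the appendices disprove 5%. They do not. Appendix 2 reports a 5.1% composite with small burrs, and Sections 1 and 6.1 describe practice moving to smaller burrs. Three of the seven studies above are at or below 5.0%. The definitions of severe dissection differ between sources, and Appendix 1 does not grade its dissections, so not every rate need match the registry's endpoint. The review article cited in Section 10.1.1 is not available here.

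This makes 5% possible, but not well supported as a single planning value. The fitting studies are small. The 5.1% comes from the trial whose overall composite is 12.1%. For 12.7% (large) and 5.1% (small) to average to 12.1%, about (12.1 − 5.1) / (12.7 − 5.1) = 92% of patients would have to be in the large-burr group, so these figures are hard to read together. The endpoint as worded covers all RA-related complications, which favours a wider count.

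**Consequence.** No decision rule depends on the width, and the registry reports estimates with intervals. That limits the harm to a misstated precision.

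**Conclusion.** The point holds as a weakness in the planning rate, not as an error in the number 1000. The protocol offers its appendices as justification for 5%, and most of the data in them lie above it. Over the range they span, about 5% to 12%, the expected width runs from 3.02 to 4.52 points with 800 evaluable and from 2.70 to 4.04 with 1000. With all patients evaluable the target survives the low Appendix 2 sum (2.99 at 6.2%) but not 7.0% or more.

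This rests on three assumptions: the simple asymptotic interval that the plan uses; no overlap between components in the 6.2% and 10.4% sums; and comparability of the cited dissection rates with the registry's endpoint. That complications are recorded around the procedure, so that 1000 rather than 800 is the relevant denominator, is an inference from Sections 7.2 and 10.2. Section 8.1 gives no window, and device events are collected for 12 months.

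**What to change.** Keep 1000 and revise Sections 10.1.1 to 10.1.3:

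1. State which components make up the primary safety endpoint and its time window, and say how the planning rate follows from the appendices.
2. Replace the single 3% claim with expected widths over a range. Possible text:

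> With 1000 patients enrolled, the expected width of the two-sided 95% confidence interval for the RA-related complication rate is 2.7 percentage points at a true rate of 5%, 3.0 at 6.2%, 3.8 at 10.4% and 4.0 at 12.1% if all are evaluable. If 800 are evaluable, the widths are 3.0, 3.3, 4.2 and 4.5.

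3. Once the window is confirmed, state that loss before the 12-month call need not reduce the denominator for complications recorded around the procedure, consistent with the safety set in Section 10.2.
4. Show the inflation step, and note that strict inflation of 811 gives 1014, rounded to 1000.

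Do not add a binomial width for 12-month outcomes on 800 completers. The protocol gives 5% only as a complication rate, and Section 10.6 uses Kaplan-Meier estimates, to which patients lost early contribute until censoring.

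The cost is a wording change with no extra patients. The downside is that the stated precision becomes less favourable.

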10.2 Statistical analysis of data set

Full analysis set (FAS): Refers to the set of analysis established in accordance to intention-to-treat (ITT) principle. All subjects who signed informed consent form and met all the inclusion criteria with the use of RA with or without other calcium debulking therapies will be included in this analysis. For subjects who are unable to complete the study follow-up, the primary endpoint will be based on the last observation carry forward method.

Per-protocol set (PPS): Refers to the set of analysis pertaining to the whole treated study population who have completed the study excluding those not fulfilling selection criteria or use of devices/ equipments not provided in this research study.

Safety analysis set (SS): Refers to all study subjects that have been evaluated at least once for safety outcome. Those with missing data will not be carried forward.

Efficacy analysis will be carried out based on the full analysis set and the per-protocol set.

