Proposed study countries/ Sites	
 1. Singapore: National Heart Centre Singapore, National University Hospital, Tan Tock Seng Hospital 2. Japan: Kokura Memorial Hospital, Sapporo Cardiovascular Clinic, Sendai Kousei Hospital 3. Malaysia: Serdang Hospital, Cardiac Vascular Sentral Kuala Lumpur 4. Thailand: Central Chest, King Chulalongkorn 5. Vietnam: Cho Ray Hospital, Bach Mai Hospital
Patient selection	
Inclusion Criteria
 
Subjects MUST fulfill ALL the following requirements in order to be eligible for the study:
 
 1. At least 21 years of age of any gender 2. Able to understand and sign an informed consent form 3. Presence of clinical indication for PCI and/or stent placement 4. Subjects willing to comply with all research and follow-up requirements 5. Angiographic criteria (ONE of the following criteria MUST be met)

[figure not shown]
	
 a. Target lesions visually have at least moderate calcifications* b. Target lesion balloon dilatation failure c. Inability of devices (microcatheters, balloons, stents or imaging devices) to pass through the target lesion d. Intravascular imaging shows severe calcification* 
6. Procedural criteria
 
 a. All patients treated with RA with or without other forms of debulking therapy 
* Moderate calcification is defined as radio-opacities noted only during cardiac cycle prior to contrast injection whereas severe calcification is defined as radio-opacities seen without cardiac motion prior to contrast injection, usually affecting both sides of the arterial lumen¹

Study duration	2-year recruitment period with a minimum 1-year of clinical follow-up. Patients will be enrolled into the study at the point of treatment with rotational atherectomy
Primary efficacy endpoint	Procedural success defined as < 20% residual stenosis in treated segment without on-table mortality with TIMI 3 flow
Primary safety endpoint	All rotational atherectomy related complications

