Sub-group analysis	
This study will evaluate real world clinical outcomes of all enrolled patients who have undergone calcium debulking therapies. The following sub-groups listed below (but are not limited to) may be used for further analysis:
 
 (i) Acute coronary syndrome (ii) Lesion length (iii) Bifurcation lesions (iv) Multiple overlapping stents (≥ 2 stents for each epicardial coronary artery) (v) Chronic kidney disease (vi) Multivessel disease (≥ 2 vessel CAD) (vii) Left main (LM) equivalent (viii) Chronic total occlusions (CTO) (ix) Severely impaired LVEF i.e. $\leq 30\%$ (x) IVUS subgroup
Primary site	National Heart Centre Singapore (NHCS)

Study flow chart

Data collection schedule

	Baseline	Follow-up
Time	≤ 48h after PCI	12m
Visit timeline	V _{start}	V _{end}
Informed consent	X	
Entry criteria	X	
History / demographic data	X	
Symptoms (CCS score)	X	X
Laboratory [^]	X	
DAPT use data*		X
Adverse events recording	X	X

Note:

Laboratory testing: full blood count, liver function (ALT, AST), renal function (BUN, creatinine), lipids (total cholesterol, LDL cholesterol, HDL cholesterol, triglycerides), glucose, coagulation panel (APTT/PT), myocardial injury markers include: CK, CK-MB, TnT / TnI.etc.

* DAPT recommendations may differ based on clinical situation/ stent use. Data collected will be type of antiplatelets and recommended duration for each antiplatelets used.

Note: All subjects will be followed up 12 months post PCI via telephone consult to check on symptoms, compliance, and development of adverse events. Medical records will also be reviewed at the end of 12 months for any clinically significant events.

Table of Contents

1. Research background -----	15
1.1 Introduction to disease-----	16
1.1.1 Disease Profile -----	16
1.1.2 Epidemiology and risk factors -----	16
1.1.3 Pathophysiology and classification -----	16
1.1.4 Detection of CAC -----	16
1.2 Introduction to treatment-----	17
1.2.1 Rotational atherectomy-----	17
1.3 Introduction to equipment-----	17
1.3.1 Structure and basic principle of ROTABLATOR™-----	17
1.3.2 Principle-----	19
2. Study Aim -----	20
3. Selection and exit criteria -----	20
3.1 Inclusion criteria-----	20
3.2 Exclusion criteria-----	21
3.3 Exit criteria-----	21
3.4 Early termination -----	21
3.4.1 Study termination criteria -----	21
3.4.2 Study site termination criteria -----	22
4. Study design-----	22
4.1 Research design-----	22

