3.2 Exclusion criteria

1. Patient unable to or decline to give consent

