4.1 Research design

This is a prospective observational multicenter cohort study of all patients with calcified coronary lesions undergoing RA in participating centres across Asia. Patients will be required to provide informed consent for data collection, including follow-up data and uploading of data on a web-based data collection platform (de-identified).

Operators/ institution coordinators will fill up hardcopy or electronic (web-based) forms including patient's baseline demographics, co-morbidities, clinical data, laboratory test results, echocardiography results, coronary angiography findings with subsequent interventions performed as well as follow-up clinical and laboratory results.

Note that while detailed data for individual patients will only be collected if there is informed consent, data from each institution will also be collected for aggregate data regarding procedural volume (eg. total cases with debulking therapy and specifically for ROTABLATOR™). This will give a sense of representativeness of data collected. This screening data will also include the following fields: age, gender, ethnicity, co-morbidities, target vessel, prior revascularization (PCI/CABG), clinical presentation, procedural urgency, angiographic procedural details (RA and PCI) and in-hospital complication and mortality. The use of this retrospective data will require appropriate approval and will only utilize anonymized data. Only in-hospital data will be obtained and no follow up data is required from these controls.

Should these data not be available in any of the participating sites, a minimum baseline demographics, procedural and inpatient outcome data with reasons for non-participation in registry should be provided for records purposes. This shall be accepted as a limitation of the study. Sub-site analysis may be performed in centres with availability of all data in this group of patients to address generalisability of the data collected.

[figure not shown]

Figure 6: Data collection workflow for (i) patients who provide consent vs (ii) patients who declined to provide consent/ unable to give timely consent in view of unexpected demise

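### The analysis sets hold only consented patients, consent may follow PCI by up to 48 hours, and deaths before consent enter no planned estimate, so in-hospital death is biased downward

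*Protocol*

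**What the plan says.** **When consent is taken.** The data collection schedule in the Protocol synopsis ticks informed consent in the baseline column, timed "≤ 48h after PCI". Section 4.2.1, the index visit within 48 hours of PCI, asks for the study consent signature there, separately from the procedural consent. Section 11.5 requires consent before inclusion in the study, without saying before the procedure, and only the participant may sign. The synopsis (Study duration) says "Patients will be enrolled into the study at the point of treatment with rotational atherectomy".

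**Who is analysed.** The sole exclusion in Section 3.2 is "Patient unable to or decline to give consent". In Section 10.2 the full analysis set is "All subjects who signed informed consent form and met all the inclusion criteria with the use of RA", with or without other debulking. The per-protocol set is those who completed the study. The safety set "Refers to all study subjects that have been evaluated at least once for safety outcome". Section 9.1 records full data for "All participants who have signed the study consent form and are eligible for participation".

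**Who is foreseen to be missing.** The Figure 6 caption in Section 4.1 describes a second stream, which includes patients "unable to give timely consent in view of unexpected demise". For non-consented patients Section 4.1 plans anonymised in-hospital data, including complications and mortality. Where a site lacks these, "a minimum baseline demographics, procedural and inpatient outcome data with reasons for non-participation in registry should be provided". Section 4.3 lists the primary outcome, death, periprocedural MI, perforation and no-reflow for patients outside the registry. The stated uses are representativeness and an optional sub-site analysis of generalisability.

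**The concern.** Section 4.1 describes a cohort of all patients with calcified lesions who undergo rotational atherectomy (RA), and Section 10.2 calls the full analysis set intention-to-treat. Yet where consent follows PCI, membership depends on surviving the treatment long enough to sign. Each RA-treated patient who dies first leaves both numerator and denominator, which necessarily lowers the in-hospital death rate. For the same patients an on-table death, which Section 7.1 counts as failure, cannot count against procedural success.

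The consented data cannot show the size of this bias, and more patients do not shrink it. It matters because the study hypothesis is that RA is a safe adjunct, and in-hospital death is the outcome on which early loss acts most directly. The 1-year Kaplan-Meier curves in Section 10.6 lose the same deaths.

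**Working it through.** **The plan's own figure.** Section 10.1 assumes 5% RA-related complications and a two-sided 95% interval of total width 3%. The simple asymptotic formula gives n = 4 × 1.96² × 0.05 × 0.95 / 0.03² = 811, as in Table 1. With 20% dropout this becomes 811/0.8 = 1014, or 811 × 1.2 = 974 by the simpler inflation. Both agree with the stated 1000 to within 3%. The sample size is not in dispute.

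**Starting rate for death.** Pooling the 13 rows of Appendix 1, Σ(n × rate)/Σn = 102.2/16,469 = 0.62%. Without the row of 13,335 it is 22.2/3,134 = 0.71%. The table does not define the period of death. I take a true in-hospital rate of 0.6%, or 6 per 1000 RA patients, as an assumption.

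**In-hospital death.** If a share q of the 6 deaths precedes consent, the consented-only rate is 6(1 − q)/(1000 − 6q):

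| q | Reported rate |
|---|---|
| 0 (all consent before PCI) | 0.60% |
| 10% | 0.54% |
| 25% | 0.45% |
| 50% | 3/997 = 0.30% |
| 100% | 0/994 = 0% |

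In general, with true rate p, the reported rate is p(1 − q)/(1 − pq), so the relative understatement is close to q. At q = 50%, a true 1.0% reads 0.50% and a true 4.0% (the highest row of Appendix 1) reads 2.04%. Exact 95% intervals are 0.22–1.30% for 6/1000 and 0.06–0.88% for 3/997.

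**1-year death, 3 early deaths lost.** An assumed true 3% reads 27/997 = 2.71%, 5% reads 47/997 = 4.71%, and 10% reads 97/997 = 9.73%. The relative bias is about 10%, 6% and 3%, against 50% for in-hospital death.

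**Procedural success, assumed true 950/1000.** If 3 lost deaths were all failures, 950/997 = 95.29%. If 6 were, 950/994 = 95.57%. If all 6 had been successes, 944/994 = 94.97%.

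**RA-related complications, true 50/1000, 6 deaths lost.** If none of the six had a complication, 50/994 = 5.03%. If three had, 47/994 = 4.73%. If all had, 44/994 = 4.43%. All lie inside the planned 3.5–6.5% interval.

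**A tempting repair that fails.** Suppose only the early deaths are added back to the consented group. With 3 early deaths, and a share c of the 997 survivors to consent agreeing (independently of later death), the rate is (3c + 3)/(997c + 3). This gives 0.63% at c = 0.9, 0.73% at c = 0.7 and 0.90% at c = 0.5, so it overstates. Using all RA patients gives 6/1000 = 0.60% for any c.

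**The case against.** The strongest reply has four parts.

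1. **The protocol has already dealt with this.** It names the group, collects its in-hospital outcomes and foresees a generalisability analysis; a supplementary estimate is ordinary SAP content, and the SAP is not at hand. The data collection is a real mitigation and makes the remedy feasible. But the protocol itself fixes the consented-only set, and that rule gives the biased result.

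2. **The analysis set for death is not stated.** Section 10.2 ties only the efficacy analysis to the full analysis and per-protocol sets, and the safety set says study subjects. This is fair: that safety subjects are consented is an inference from Sections 3.2, 9.1 and 11.5. It is nevertheless the natural reading, since someone excluded for want of consent is hardly a study subject.

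3. **The 48-hour heading may be a data-capture window, with consent usually taken earlier.** This stands as a limit on size: patients consented beforehand are unaffected. It does not remove the problem, because a treated patient can die before consenting only if consent may follow treatment, and Figure 6 foresees exactly that.

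4. **The effect is small and within sampling error.** The primary endpoints do move little, and 0.30% lies inside the interval for 6/1000. But sampling error shrinks with enrolment, and this bias does not.

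**Conclusion.** The concern holds. Followed as written, the plan biases in-hospital death downward, by a relative amount close to the share of in-hospital deaths that precede consent. That share, and the proportion of patients consented after PCI, are not in the protocol, so the size is unknown. On an assumed true rate of 0.6%, the reported rate would be 0.45% to 0.30% if a quarter to a half of deaths come first; if all consent is taken before PCI, there is no bias from this source. The 1-year curves carry the same loss with smaller relative effect. Procedural success is raised by lost on-table deaths, and RA-related complications are lowered only if the lost patients had them more often than others; neither shift is material here. It should be fixed, but it does not threaten the sample size or the primary estimates.

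**What to change.** In Section 10.2, add an in-hospital estimate of death, procedural success and RA-related complications for all RA-treated patients, shown beside the consented-only result. It should include every non-consented RA patient, both those who declined and those who died first, from the Section 4.1 and 4.3 records, at sites where approval and data allow. Adding only the early deaths should be ruled out, for the reason shown in the working. Where individual records are missing, use the site's aggregate RA count as denominator and its RA in-hospital deaths as numerator, or report the result as a bound.

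Report the number of deaths before consent by site. State that the consented-only results and the 1-year curves are conditional on survival to consent; no all-RA 1-year estimate is possible, because Section 4.1 collects only in-hospital data on non-consented patients. Reconcile consent and enrolment timing across the synopsis (Study duration), the data collection schedule, Section 4.2.1 and Section 11.5.

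The cost is wording and one added analysis of records already planned. The approval that Section 4.1 foresees must cover outcome estimates, including for patients who declined, and this may need checking at each site. Some sites may supply only minimum data. The Section 4.3 list is thinner than Section 4.2.1 (no angiogram copies, post-procedural ECG or burr data), so RA-related complications may be incompletely captured. Aggregate counts are of procedures, so a patient with staged RA may count twice. These limits are why the two estimates belong side by side.
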